## ANALYSIS POPULATIONS

This study will enroll approximately 300 MF-CTCL patients who are being treated (newly initiated or continuing treatment) with Valchlor from up to 50 participating university-affiliated hospitals, community hospitals, or community clinics in the United States.

Patients considered 'being treated with Valchlor' are composed of two distinct groups:

- 1) Patients who are newly initiating Valchlor treatment (i.e. patients who have initiated Valchlor within 30 days or fewer prior to enrollment) and,
- 2) Patients who are continuing treatment with Valchlor (i.e. patients who have been on Valchlor for more than 30 days prior to enrollment).

Patients in either group must be treated with Valchlor at enrollment to be eligible for the study.

All consecutive MF-CTCL patients who are receiving Valchlor at participating US centers are eligible for enrollment in the study, regardless of other MF-CTCL therapies received before or at the time of enrollment.

The primary efficacy endpoint will be the proportion of subjects who are responders to treatment at the 12-month timepoint using a  $\geq 50\%$  reduction from baseline in BSA as the definition of a responder in the group of patients who used mechlorethamine plus corticosteroids and possibly another treatment. Since PROVe did not require a specific visit schedule, the primary 12-month analysis will include patients with a post-baseline % BSA score that falls within a window of  $365 \pm 90$  days. Please note that in this observational trial, patients continued on study even if they permanently discontinued mechlorethamine gel for any reason and switched to new therapy. Given this, such patients (15-20%) will be excluded from the analysis at 12 months. A sensitivity analysis will be conducted for the primary analysis using the full dataset. We will compare this to the subset of patients who discontinued mechlorethamine gel (Table 21a).

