The by-time analyses for each visit will provide supportive clinical and statistical mechlorethamine response data over the whole treatment period, before and after the 12 month results. Patient visits were variable throughout the study and no defined patient visits were required in PROVe. Given this construct, the By-Visit analyses of % BSA data, Pruritis VAS, Skin-Dex 29, and the MF/SS CTCL QOL instrument will be constructed from the respective change from baseline that occurred closest to each of the following timepoints 1, 3, 6, 9, 12, 15, 18, 21 and 24 months, and will include data that falls within  $\pm 45$  days of each designated timepoint.

Other secondary endpoints include:

- Overall Response Rate 2 (ORR2) Percent of patients with  $\geq 50\%$  reduction from baseline in % Body Surface Area of disease for at least two consecutive visits.
- Overall Response Rate 4 (ORR4) Percent of patients with  $\geq 50\%$  reduction from baseline in % Body Surface Area of disease for at least four consecutive visits.
- Time to Next Treatment (TTNT). TTNT is defined as the median number of days an individual patient stayed on a treatment before starting a new treatment or adding on an additional treatment.
- Rates of on Study Hospitalization
- Pruritis VAS
- SkinDex-29

- MF/SS CTCL – QOL Instrument

For each endpoint, separate analyses will be done for patients contributing data with IA and IB staging, all staged patients, and all patients regardless of staging. As PROVe is an observational study, an Intent-to-Treat (ITT) population analysis is not applicable. There are no cases where an intention to treat was prevented and therefore no potential for a selection bias in the analyses prespecified in this SAP. This results in a total of 51 analysis types as shown in the Figure 1 below.

Figure 1: Analysis Populations for the PROVe Study

	Patients Contributing Data			Totals:
	IA and IB Staging	All Staged	All Patients with and without Staging	
Primary Endpoint	1	1	1	3
9 By-Time Analyses	9	9	9	27
7 Other Secondary Endpoints	7	7	7	21
			Overall Total:	51

These analyses will be applied to following four (4) analysis populations:

1. Valchlor + corticosteroids + possibly another treatment (primary) (V+C+other)
2. Valchlor + phototherapy + possibly another treatment (V+P+other)
3. Valchlor + oral bexarotene + possibly another treatment (V+B+other)
4. Valchlor + any other treatment (V+other)

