## ASSESSMENT SCHEDULE

Demographics, medical history, current and historical MF-CTCL treatments, clinical status by physician, clinical status assessments, the Visual Analogue Scale (VAS) for pruritus, the Skindex-29, and ongoing adverse events (AEs) and serious adverse events (SAEs) related to Valchlor are collected at the enrollment visit, per routine clinic visits. Any data that is not collected at enrollment or present in the historical patient information will be indicated as not assessed, not applicable or not done, as appropriate. In addition, to appropriately construct change from baseline analyses all baseline data must be verified as such. For example, if a % BSA score is provided at enrollment, it may not represent a baseline disease score if a subject was already using mechlorethamine prior to the collection of that score. The same handling should apply to the PRO questionnaires.

Change in TNMB classification, change in medical history, change in medications with Valchlor and other MF-CTCL treatments, HCU, clinical status by physician, clinical status assessments, VAS for pruritus, the Skindex-29, reports of secondary exposure, and all AEs and SAEs related and unrelated during Valchlor use and >30 days after Valchlor discontinued are collected at follow-up visits during the observation period, as recorded during the routine clinic visit. These visits occur at the physician's discretion (i.e., they are not scheduled per protocol); consequently, the number of follow-up visits will vary across patients. Additionally, the data collected during the visits will be dependent upon routine clinic practice, and thus not all data may be available.

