### **Exposure Definitions and Measures**

Start of observation is defined as date of enrollment.

End of observation is defined as End Of Study (EOS), which includes, adverse event, patient withdrew consent, patient lost to follow-up, physician's decision to withdraw or study completion, whichever occurs first.

Total exposure time is defined as the date of first Valchlor exposure to the date of last Valchlor exposure.

Total on-study Valchlor exposure time is defined as the first day of Valchlor use to last day of Valchlor use during the observation period. If the patient was using Valchlor at the end of observation, the last on-study day of Valchlor use is equal to the end date of observation period.

Patients may discontinue Valchlor while on study. In this case, the last day of Valchlor exposure will be when the patient discontinues Valchlor (as reported on the Valchlor treatment log). Patients who restart Valchlor after discontinuing will then begin adding Valchlor exposure days once Valchlor is restarted through the end of the study. For the patients that restart Valchlor during the study, the Total on-study Valchlor exposure will be a sum of all days in which Valchlor was dosed during the study, as reported on the Valchlor treatment log.

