	IA and IB Staging	All Staged	All patients with and without Staging
	N=	N=	N=
V+C+Other			
V+P+Other			
V+OB+Other			
V+C+P+Other			
V+C+P			
V+Other			

Table 21a. Percent of patients with  $\geq 50\%$  reduction from baseline in % Body Surface Area of disease in 12 months – All Patients

Helsinn Therapeutics (US), Inc.,  
 Protocol AC-079A501 (PROVe)

Table 22. Percent of patients with  $\geq 50\%$  reduction from baseline in % Body Surface Area of disease at each visit preceding and following the 12 month visit, including months 1, 3, 6, 9, 12, 15, 18, 21 and 24  $\pm$  45 days.

	IA and IB Staging	All Staged	All patients with and without Staging
Month 1	N=	N=	N=
V+C+Other			
V+P+Other			
V+OB+Other			
V+C+P+Other			
V+C+P			
V+Other			
Month 3	N=	N=	N=
V+C+Other			
V+P+Other			
V+OB+Other			
V+C+P+Other			
V+C+P			
V+Other			
Month 6	N=	N=	N=
V+C+Other			
V+P+Other			
V+OB+Other			
V+C+P+Other			
V+C+P			
V+Other			
Month 9	N=	N=	N=
V+C+Other			
V+P+Other			
V+OB+Other			
V+C+P+Other			
V+C+P			
V+Other			
Month 12	N=	N=	N=
V+C+Other			
V+P+Other			
V+OB+Other			
V+C+P+Other			

V+C+P			
V+Other			
Month 15	N=	N=	N=
V+C+Other			
V+P+Other			
V+OB+Other			
V+C+P+Other			
V+C+P			
V+Other			
Month 18	N=	N=	N=
V+C+Other			
V+P+Other			
V+OB+Other			
V+C+P+Other			
V+C+P			
V+Other			
Month 21	N=	N=	N=
V+C+Other			
V+P+Other			
V+OB+Other			
V+C+P+Other			
V+C+P			
V+Other			
Month 24	N=	N=	N=
V+C+Other			
V+P+Other			
V+OB+Other			
V+C+P+Other			
V+C+P			
V+Other			

Helsinn Therapeutics (US), Inc.,  
 Protocol AC-079A501 (PROVe)

Table 23. Overall Response Rate 2 (ORR2) Percent of patients with  $\geq 50\%$  reduction from baseline in % Body Surface Area of disease for at least two consecutive visits

	Patients Contributing Data		
	IA and IB Staging	All Staged	All patients with and without Staging
	N=	N=	N=
V+C+Other			
V+P+Other			
V+OB+Other			
V+C+P+Other			
V+C+P			
V+Other			

Helsinn Therapeutics (US), Inc.,  
 Protocol AC-079A501 (PROVe)

Table 24. Overall Response Rate 4 (ORR4) Percent of patients with  $\geq 50\%$  reduction from baseline in % Body Surface Area of disease for at least four consecutive visits

	Patients Contributing Data		
	IA and IB Staging	All Staged	All patients with and without Staging
	N=	N=	N=
V+C+Other			
V+P+Other			
V+OB+Other			
V+C+P+Other			
V+C+P			
V+Other			

Helsinn Therapeutics (US), Inc.,  
 Protocol AC-079A501 (PROVe)

Table 25. Time to Next Treatment (TTNT)

	Patients Contributing Data		

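### The uniform ±45-day window lets one visit fill both the Month 1 and Month 3 rows, and the Month 1 window reaches back past day 0

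*SAP*

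**What the plan says.** The by-time rule is in the SAP under Analysis Populations: "the By-Visit analyses of % BSA data, Pruritis VAS, Skin-Dex 29, and the MF/SS CTCL QOL instrument will be constructed from the respective change from baseline", with the value chosen as the one "closest to each of the following timepoints 1, 3, 6, 9, 12, 15, 18, 21 and 24 months". Eligible data lie within ±45 "days of each designated timepoint". The Table 22 shell in Appendix A repeats the same half-width for response "at each visit preceding and following the 12 month visit, including months 1, 3, 6" and the later months. The SAP adds that "Patient visits were variable throughout the study and no defined patient visits were required in PROVe", so a visit can fall on any day.

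Three other statements bear on the point:

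- For the primary endpoint, Analysis Populations says "the primary 12-month analysis will include patients with a post-baseline % BSA score that falls within a window of" 365 ± 90 days. The post-baseline condition appears there and not in the by-time rule.
- Assessment Schedule warns that where a % BSA score was taken at enrollment, "it may not represent a baseline disease score if a subject was already using mechlorethamine prior to the collection of that score".
- Exposure Definitions and Measures says "Start of observation is defined as date of enrollment", but nothing makes that date day 0 of the windows.

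The SAP gives no separate Month 1 window, no lower bound at day 1, no rule that a visit serves only one timepoint, and no number of days per month.

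**The concern.** A half-width of 45 days suits timepoints a quarter apart. Month 1 does not fit that spacing: it lies about two months before Month 3 and less than 45 days after day 0. Two things follow. The same assessment can represent a patient at both Month 1 and Month 3. And the Month 1 window takes in days on which no follow-up under the windowed schedule has yet happened.

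At stake is the early course of % BSA response, pruritus VAS, Skindex-29 and the CTCL QOL score. Reused values flatten the apparent difference between the first two rows. A baseline value entered as Month 1 would pull response and mean change toward zero. Either route also adds to the N of a row, and the SAP uses N=20 as its threshold for running a statistical analysis.

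**Working it through.** **Inputs.** Timepoints 1, 3, 6, ..., 24 months and the ±45 days come from SAP Analysis Populations and the Table 22 shell. Days per month are an assumption: 365/12, in line with the SAP's own 365 days for 12 months, with 30 and 28 tried as alternatives. The SAP lists no day ranges, so there is no stated figure to reproduce.

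**Windows.** Target = months × days per month, rounded. Window = target ± 45. Shared days = upper bound of the earlier window - lower bound of the later one + 1.

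| Days per month | Month 1 | Month 3 | Shared by Months 1 and 3 | Shared by Months 3 and 6 |
|---|---|---|---|---|
| 365/12 | 30 ± 45 = -15 to 75 | 91 ± 45 = 46 to 136 | 75 - 46 + 1 = 30 | none |
| 30 | 30 ± 45 = -15 to 75 | 90 ± 45 = 45 to 135 | 75 - 45 + 1 = 31 | 1 (day 135) |
| 28 | 28 ± 45 = -17 to 73 | 84 ± 45 = 39 to 129 | 73 - 39 + 1 = 35 | 7 (days 123-129) |

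From Month 3 on, targets are 3 × 365/12 = 91.25 days apart. Half of that is 45.6, just over 45, so the later windows do not overlap with 365/12-day months. With 30-day months each adjacent pair shares one boundary day.

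**Does the closest-value rule prevent reuse?** Apply it with targets at days 30 and 91:

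- Follow-up on day 50 only: it is 20 days from Month 1 and 41 from Month 3, so it fills both rows.
- Follow-up on days 60 and 150, day 0 not eligible: day 60 is 30 and 31 days from the two targets, so it fills both.
- Follow-up on days 35, 60 and 91: day 35 fills Month 1, day 91 fills Month 3, and day 60 is not used. There is no reuse.

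Reuse therefore needs a visit in the shared days that is the closest eligible value to both targets.

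**Can day 0 enter Month 1?** Day 0 is 30 days from the Month 1 target, within the 45 allowed. With visits on days 0, 90 and 180, day 90 is 60 days away and out of the window, so day 0 is the only candidate. If day 0 is eligible it fills Month 1; if not, the cell is empty.

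**The two gaps interact.** A visit on day v is v - 30 days from the Month 1 target, so an eligible day 0 value beats it once v exceeds 60. With visits on days 0 and 70, the literal rule puts day 0 in Month 1 and day 70 in Month 3. Adding only the post-baseline condition puts day 70 in both. Both gaps need closing.

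**Illustration of dilution.** If a fraction f of a Month 1 row were baseline values with zero change, the response rate would become (1 - f) times its value among the rest. For an assumed 20% rate and assumed f of 10%, 25% or 50%, the row would show 18%, 15% or 10%. These fractions are not in the documents.

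**The case against.** The best reply concerns day 0. The rule selects a change from baseline, and a baseline value minus itself is not naturally one. The SAP says post-baseline for the parallel 12-month % BSA analysis and asks that baseline data be verified. On that reading there is only a wording gap. This largely stands: the text permits a day 0 value but does not show that one would be used.

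A reader might go further and infer that Month 1 would be filled with values whose change is zero by construction. The documents do not support that. It needs day 0 to be the baseline assessment itself, which is nowhere stated. Patients must already be on Valchlor at enrollment. If baseline is the pre-Valchlor score and the windows run from enrollment, the enrollment value is an on-treatment change that need not be zero.

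A reader might also infer that every visit on days 46-75 is counted twice. The day 35, 60 and 91 example shows otherwise.

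Finally, the Month 1 and Month 3 rows are reported separately and not pooled, the by-time analyses are supportive, and p-values are descriptive. So no single estimate is double-weighted. That is correct and limits the importance of the point, but the two rows would still be less distinct than their labels suggest.

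**Conclusion.** The overlap is established: about 30 days are common to Months 1 and 3, it persists under every month length tried, and the closest-value rule does not stop one visit from filling both rows. The day 0 part is the weaker half. It is an omission that allows an enrollment or baseline value into Month 1, with zero change only if that value is the baseline itself.

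It is tempting to add the 16 days from -15 to 0 to the 30 shared days and call 46 of the 91 window days, about half, unusable. That counts calendar days, not patients. Few or no follow-up visits can fall before day 0 if day 0 is enrollment, and the shared days are only potentially reused. The documents give no distribution of visit times, so the number of patients affected cannot be determined.

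The effect is confined to the Month 1 and Month 3 rows of Tables 22 and 27a-c. The primary endpoint has its own window, and ORR2, ORR4, time to next treatment and hospitalization rates do not use these windows. The day ranges rest on 365/12-day months. The point should be corrected, but it does not threaten the main result.

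**What to change.** In SAP Analysis Populations and the Table 22 shell:

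1. Define day 0 for the windows, and say how the enrollment score is treated when baseline is a pre-Valchlor score.
2. Require a post-baseline assessment for every by-time row, as the primary analysis already does.
3. Split Months 1 and 3 at their midpoint, (30 + 91)/2 = 60.5: for example Month 1 = days 1-60 and Month 3 = days 61-136.
4. State that each visit is assigned to one timepoint only.
5. State the days-per-month convention, so that later windows share no boundary day. With 365/12-day months the later windows can stay as they are.

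The cost is a few sentences and a small programming change. The Month 1 or Month 3 rows will hold somewhat fewer patients, and a row near the SAP's threshold of 20 could fall below it. How many patients would be lost cannot be judged from the documents.

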5 RESEARCH METHODS

5.1 Study design

This is a multi-center, prospective, observational study of MF-CTCL patients who have newly initiated Valchlor or who are continuing treatment with Valchlor.

Patients will be followed by their physician according to routine clinical practice. With the exception of protocol-required patient-completed questionnaires, there are no specific or mandated clinical assessments to be performed, and patients will not receive experimental intervention or treatment as a consequence of their participation in this study. The study protocol will not mandate any specific schedule of visits. Patients will undergo clinical assessments and receive standard medical care as determined by the patient's physician in a real-world setting.

Patients will be followed prospectively for a maximum of 2 years from the date of signed informed consent until end of study (EOS), which includes withdrawal of consent, loss to follow-up, death, or study completion. Continuation in the study is not contingent on continuation of Valchlor.

The study will end after all enrolled patients have been followed for 2 years, or discontinued from the study for any reason.

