5.9 Discussion of the study methods (including limitations)

This study is an observational, prospective study examining MF-CTCL patients being treated with Valchlor in a real-world clinical setting. Valchlor treatment will be based on prescriber decision and will not be influenced by participation in this study. The patients will be followed by their physician according to routine clinical practice. The study protocol does not mandate any treatment, procedures or visits. Patient-completed questionnaires, however, are a study requirement and will be administered at all study visits for patients who can read and understand English, and are physically and mentally able to complete the questionnaires based on the investigator's assessment.

Any interpretation of observational study results should consider limitations to observational real-world study designs, including potential sources of selection or information biases, and confounding factors.

To minimize selection bias, participating centers will offer enrollment in the study to all consecutive MF-CTCL patients currently treated with Valchlor [see Section 5.2.1 for inclusion criteria], regardless of other MF-CTCL specific therapy received before or at

the time of enrollment, or during the study. This study collects data on all users of Valchlor. At enrollment, a review of existing medical records will be performed to collect information as described per [Table 1](#) (enrollment visit). Thereafter, all data will be collected during the observation period.

Patients who are enrolled under the original protocol prior to protocol Amendment 1 and are still ongoing in the study will be re-consented under Amendment 1 and will continue to follow the schedule of Table 1 eCRF Data Collection specified in this protocol up to end of study (Month 24). Patients who enrolled and have completed 1 year of the study under the original protocol will not be offered to continue in the study and thus not re-consented under Amendment 1.

To minimize the number of patients lost to follow-up, there will be regular contact with patients by the site, including 3 attempts to contact a patient before she/he is considered lost to follow-up.

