### **Secondary Analyses will include:**

- Percent of patients with  $\geq 50\%$  reduction from baseline in % Body Surface Area of disease at each visit preceding and following the 12 month visit
- Overall Response Rate 2 (ORR2) Percent of patients with  $\geq 50\%$  reduction from baseline in % Body Surface Area of disease for at least two consecutive visits.
- Overall Response Rate 4 (ORR4) Percent of patients with  $\geq 50\%$  reduction from baseline in % Body Surface Area of disease for at least four consecutive visits. Further description of the ORR4 endpoint is shown in [Prince et al 2017].
- Time to Next Treatment (TTNT). Further description of the TTNT endpoint is shown in [Hughes and Prince 2014].
- Rates of on-study hospitalization

- Change from baseline in PRO questionnaires:
  - a. Pruritis VAS
  - b. SkinDex-29
  - c. MF/SS CTCL QOL instrument

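### ORR2 and ORR4 count consecutive visits in a study with no visit schedule, so the response duration they imply depends on how often the clinic sees the patient

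*SAP*

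**What the plan says.** The SAP (Analysis Populations, and the list of secondary analyses) names two sustained-response endpoints. ORR2 is the percentage of patients with at least a 50% "reduction from baseline in % Body Surface Area of disease for at least two consecutive visits". ORR4 asks for the same "reduction from baseline in % Body Surface Area of disease for at least four consecutive visits". Neither definition gives a minimum number of days, a minimum or maximum gap between visits, or a minimum number of BSA assessments. For ORR4 the SAP refers to a publication for further description. It does not reproduce the content, and its References section lists only software. ORR2 has no such pointer.

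Both documents say that visits are unscheduled. Protocol 5.1: "The study protocol will not mandate any specific schedule of visits". SAP, Analysis Populations: "Patient visits were variable throughout the study and no defined patient visits were required in PROVe". SAP, Assessment Schedule: visits are at the physician's discretion and "consequently, the number of follow-up visits will vary across patients". The SAP section on clinical status assessments adds that no single response measure is mandated, so a visit may have no BSA.

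Follow-up also differs between patients. The maximum is 24 months, but protocol 5.9 says: "Patients who enrolled and have completed 1 year of the study under the original protocol will not be offered to continue in the study".

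Elsewhere the SAP does allow for irregular visits. The primary endpoint uses a window of 365 ± 90 days, and the by-visit analyses use ± 45 days around nine timepoints. Neither window is extended to ORR2 or ORR4.

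**The concern.** A sustained-response endpoint is read as a statement about how long response lasts. When it is defined by a visit count in a study without a schedule, the same label covers different durations in different patients. A responder seen monthly can qualify within a few months, while an equally good responder seen twice a year needs a much longer response or cannot qualify at all.

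Two things are at stake. The absolute rates could not be read as durable response. The rows of Tables 23 and 24, which set the treatment combinations side by side, could also differ because visit frequency or length of follow-up differs. In addition, several operational rules are missing, so two programmers could obtain different ORR4 values from the same data.

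**Working it through.** The documents give no expected rate, sample size or power for ORR2 or ORR4, so there is no stated figure to reproduce. Visit spacing, onset and duration below are assumptions; the definitions and follow-up lengths come from the documents.

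**1. Span implied by k visits.** At regular spacing g, k consecutive visits span (k − 1) × g. Visits after enrollment in F months number F/g, rounded down.

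| Spacing g (months) | ORR2 span, g | ORR4 span, 3g | Visits in 12 months | Visits in 24 months |
|---|---|---|---|---|
| 1 | 1 | 3 | 12 | 24 |
| 2 | 2 | 6 | 6 | 12 |
| 3 | 3 | 9 | 4 | 8 |
| 4 | 4 | 12 | 3 | 6 |
| 6 | 6 | 18 | 2 | 4 |

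The span varies sixfold for both endpoints (6/1 and 18/3).

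**2. Reachability.** ORR4 needs four post-baseline BSA values. With 12 months of follow-up and 6-monthly visits there are two after enrollment. Adding an enrollment BSA that counts as post-baseline makes three, so ORR4 cannot be met. With 4-monthly visits there are three after enrollment, and an enrollment BSA taken on Valchlor would make four (months 0, 4, 8, 12). ORR4 is then reachable if that value counts, which the SAP does not say.

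**3. Denominator.** If a share s of the denominator has fewer than four BSA values and counts as non-responding, ORR4 cannot exceed 1 − s. If the rate would otherwise be 40% (assumed), s = 10% gives 0.40 × 0.90 = 36%, s = 20% gives 32% and s = 50% gives 20%.

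**4. Same disease, different spacing.** Simulation of 200,000 patients: 60% respond, onset is uniform over months 1 to 9, duration is exponential with mean 12 months, BSA is measured at every visit, the enrollment value is not counted, and all patients are in the denominator.

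| Spacing (months) | ORR2, 24 mo | ORR4, 24 mo | ORR2, 12 mo | ORR4, 12 mo |
|---|---|---|---|---|
| 1 | 53.1% | 44.9% | 53.1% | 44.9% |
| 2 | 46.9% | 33.6% | 46.9% | 21.2% |
| 3 | 41.8% | 25.5% | 41.8% | 6.7% |
| 4 | 36.6% | 18.8% | 32.6% | 0% |
| 6 | 28.0% | 6.8% | 18.6% | 0% |

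The 0% at 4-monthly spacing depends on leaving out the enrollment value. With onset moved 4 months earlier and the enrollment visit counted, it becomes about 7%.

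**5. Number of chances.** If each visit independently has a 50% chance of showing response (assumed), the probability of four in a row is 0.5⁴ = 6% with 4 visits, 30% with 12 and 55% with 24.

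**6. Does a time-based definition help?** Same model and denominator, with illustrative minimum spans of 2 months (ORR2) and 4 months (ORR4), at least two qualifying assessments, and 24 months of follow-up. From monthly to 6-monthly visits, ORR4 runs from 41% to 28%, against 45% to 7% by visit count. ORR2 runs from 49% to 28%, against 53% to 28%. Much of the ORR4 gradient goes; most of the ORR2 gradient stays.

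**The case against.** The case on the other side has real content.

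- **Response still has to be shown.** Every counted visit must show at least a 50% reduction. A reader might infer that the endpoints measure visit frequency instead of duration. That goes too far; they mix the two.
- **The denominator is not known to be wrong.** A reader might infer that sparsely seen patients are counted as ORR4 failures. Tables 23 and 24 are headed as covering patients who contribute data, and protocol 5.7.1 limits each response analysis to patients with that measure reported. Who contributes to ORR4 is left open. If four BSA values were required, the problem would become selection of frequently seen, longer-followed patients.
- **ORR4 is not impossible for every 12-month completer with few visits.** Baseline is meant to precede Valchlor: the Assessment Schedule warns that an enrollment BSA may not be a baseline value, and shell Table 6b treats the enrollment visit as post-treatment. At 4-monthly spacing the outcome turns on that unstated rule.
- **Part of the ORR4 definition may lie in the cited publication.** Its content is not in the SAP, so whether it sets a duration or a denominator cannot be judged here.
- **Differing visit frequency between combinations is not documented.** It is plausible that patients on phototherapy or oral bexarotene are seen more often, but neither document says so. Row differences cannot be called artefact on this evidence.
- **The consequences are limited.** P-values are descriptive, the primary and by-visit BSA analyses are anchored in time, Table 1B shows visit counts, and Listing 8 shows visit dates with BSA response.

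These points narrow the claim and lower its severity. They do not supply the missing duration, denominator or rule for a visit without BSA. Reading a visit as one of the nine windowed timepoints would fix the ORR4 span at 8 to 9 months, but the SAP does not say this.

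**Conclusion.** The point holds in a limited form. As written, ORR2 and ORR4 carry no fixed duration: two visits can mean 1 to 6 months and four visits 3 to 18 months over the spacings considered. A patient with fewer than four post-baseline BSA values cannot meet ORR4; 6-monthly visits with 12 months of follow-up is a certain case. The SAP leaves three rules open: the denominator, whether an on-treatment enrollment BSA counts, and how a visit without BSA affects a run.

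The direction follows from the definitions. The size is unknown, because the documents give no distribution of visits or BSA assessments. The 45% to 7% range for ORR4 rests on the assumed disease course, regular visits and BSA at every visit, and is illustrative only. Severity: should-fix. These are descriptive secondary endpoints, and the primary endpoint does not depend on them.

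**What to change.** - **Define both endpoints by elapsed time** between the first and last qualifying BSA assessments. Set a minimum number of days for each before the rates are computed, and require at least two assessments and no intervening BSA below a 50% reduction. The 2- and 4-month spans used in the check are illustrations, not values from the documents.
- **State the open rules.** Skip visits without BSA, and say whether an on-treatment enrollment BSA counts. Write any rule taken from the cited publication into the SAP.
- **State the denominator and show two:** all patients with a baseline and a post-baseline BSA, and those with enough BSA follow-up to show the span.
- **Keep the visit-count versions as supplementary.** Beside all rates, report the number and spacing of BSA assessments per population, and caution against comparing rows, because ORR2 stays sensitive to spacing under the time-based definition too.

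The cost is SAP wording and some reprogramming from visit dates already collected; no new data are needed. The restricted denominator is smaller and selects against early terminators, which is why the unrestricted one should stand beside it.
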